5.1. Recruitment

The NAFLD Pediatric Database 2 study will build upon the population recruited in NAFLD Database by enrolling approximately 650 new pediatric participants. Enrollment of participants was initiated in December 2009 and will continue to at least April 2019. The expectation is that recruitment will come from 11 participating clinical centers with rates of recruitment varying according to the resources and patient populations of each center.

5.2. Inclusion criteria

Continuing participants previously met inclusion (and exclusion) criteria for the NAFLD Database study or the TONIC trial; these criteria are not listed here, but are in the applicable protocols for these NASH CRN studies. Both continuing and new pediatric participants must meet all of the inclusion criteria below, which are listed separately for continuing and new participants.

Continuing participants:

- Previously enrolled in the NAFLD Database study or TONIC trial
- Age at least 2 years and not older than 17 years during the consent process
- Willingness to be in the study for 1 or more years
- Ability and willingness to give written, informed parental consent and child assent, per local IRB guidelines, to be enrolled into the pediatric Database 2 study

New participants:

- Age at least 2 years of age and not older than 17 years during the consent process
- Willingness to be in the study for 1 or more years
- Ability and willingness to give written, informed parent consent and child assent to be enrolled into the pediatric Database 2 study
- Minimal or no alcohol use history consistent with NAFLD
- Having undergone a liver biopsy that is obtained within 120 days of enrollment
- Collection of biosamples (serum, plasma, DNA, and, if available, liver tissue) within 90 days prior to enrollment and 0-90 days before or 4-90 days after the standard of care liver biopsy

5.3. Exclusion criteria

Continuing participants who meet the following criterion will not be eligible:

- Any condition or circumstances, which, in the opinion of the investigator, would interfere with completion of scheduled follow-up visits and procedures for the duration of the pediatric Database 2 study

New participants who meet any of the following criteria will not be eligible:

- Total parenteral nutrition for more than 1 month within a 6 month period before baseline liver biopsy
- Short bowel syndrome
- History of gastric or jejunoileal bypass preceding the diagnosis of NAFLD. Bariatric surgery performed following enrollment is not exclusionary. Liver biopsies obtained during bariatric surgery cannot be used for enrollment because of the associated surgical or anesthetic acute changes and the weight loss efforts that precede bariatric surgery
- History of biliopancreatic diversion
- Evidence of advanced liver disease defined as a Child-Pugh-Turcotte score equal to or greater than 10
- Evidence of chronic hepatitis B as marked by the presence of HBsAg in serum (participants with isolated antibody to hepatitis B core antigen, anti-HBc total, are not excluded)
- Evidence of chronic hepatitis C as marked by the presence of anti-HCV or HCV RNA in serum
- Low alpha-1-antitrypsin level and ZZ phenotype (both determined at the discretion of the investigator)
- Wilson's disease
- Known glycogen storage disease
- Known dysbetalipoproteinemia
- Known phenotypic hemochromatosis (HII greater than 1.9 or removal of more than 4 g of iron by phlebotomy)
- Prominent bile duct injury (florid duct lesions or periductal sclerosis) or bile duct paucity
- Chronic cholestasis
- Vascular lesions (vasculitis, cardiac sclerosis, acute or chronic Budd-Chiari, hepatoportal sclerosis, peliosis)
- Iron overload greater than 3+
- Zones of confluent necrosis, infarction, massive or sub-massive, pan-acinar necrosis
- Multiple epithelioid granulomas
- Congenital hepatic fibrosis

- Cystic fibrosis
- Polycystic liver disease
- Other metabolic or congenital liver disease
- Evidence of systemic infectious disease
- Known HIV positive
- Disseminated or advanced malignancy
- Concomitant severe underlying systemic illness that in the opinion of the investigator would interfere with completion of follow-up
- Active drug use or dependence that, in the opinion of the study investigator, would interfere with adherence to study requirements
- Any other condition, which in the opinion of the investigator would impede compliance or hinder completion of study
- Inability for parent to provide informed consent and child \geq 8 years to give assent

5.4. Database 2 enrollment procedures

Clinical centers must be certified by the DCC to open enrollment in the NAFLD Pediatric Database 2 study. Prior to implementation of this protocol, the principal investigator must have the protocol, assent, and consent forms approved by his/her Institutional Review Board (IRB). Once a candidate for pediatric Database 2 study entry has been identified, study procedures will be carefully discussed with the participant and his/her family as required by the local IRB. The participant will be asked to read and sign the assent or consent form that was approved by the local IRB. There will be a separate consent for the collection, storage, and use of DNA for genetic research.

6. Schedule of visits and procedures

6.1. Screening, consent, and follow-up overview

While many of the new NAFLD Pediatric Database 2 participants may come from the current patient rosters of the NASH CRN investigators, children may be referred to the NASH CRN from physicians outside the Network and some patients may refer themselves. In addition, children may be recruited from established registries permitting patient contact for enrollment in clinical trials. Patients considered by the site investigator as likely to be eligible for enrollment as a new or continuing pediatric participant in Database 2 may be consented and screened at a visit that is part of the ongoing clinical care of the patient. Tests may be ordered and billed to insurance to appropriately complete the evaluation of liver disease and general medical condition according to a reasonable standard of care. Similarly, a standard of care liver biopsy billed to insurance will be obtained when clinically indicated to establish a diagnosis and stage the disease. Patients will be sought for participation in the pediatric Database 2 study who need or recently have had (≤ 120 days prior to enrollment) a liver biopsy to evaluate suspected NAFLD.

Patients who are thought to be candidates will be invited to be screened for enrollment in the pediatric Database 2 study. Screening will take place over two visits. At the initial screening visit, the study procedures of Database 2 participation will be introduced. If the participant is agreeable and is thought to have NAFLD or NASH-related cirrhosis, then he/she may enter the formal screening phase.

Screening and baseline data collection procedures will usually be conducted over two (or more) clinic visits completed on separate calendar days. The goal of the first screening visit is to obtain parent consent/child assent and start recording screening data regarding the study's inclusion and exclusion criteria on NAFLD Database 2 data forms. The goal of the second screening visit is to complete procedures and collection of baseline data on participants who appear to be eligible. This separation of procedures between two visits is provided as a practical guideline. Screening procedures and data collection can be organized as appropriate at each clinical center. The signing of the consent statement and the procedures during screening can occur on one day or separate calendar days and may occur over a period of up to 90 days. Baseline etiologic tests may not need to be repeated in continuing pediatric participants if there have been no substantial changes in risk factors to explain the etiology of liver disease.

Consent for screening and HIPAA authorization to disclose protected health information with the NAFLD Pediatric Database 2 study must be obtained from the participant and parent prior to initiating any data collection for the NAFLD Database 2 study; this consent and authorization must be obtained at the start of the initial screening visit. The consent will include a parent consent and a child assent for more general screening and enrollment in the pediatric Database 2 study, including follow-up for the duration of the study. Parent consent for the collection, storage, and use of blood

samples for current and future genetic research will be obtained separately. HIPAA authorization forms will be prepared according to clinical center IRB requirements and guidelines.

Minimum follow-up on a participant will be 48 weeks, and maximum follow-up on a participant will be 480 weeks. Data will be collected during screening (2 visits) and at yearly intervals thereafter (a maximum of 12 visits). Appendix 10.3 displays the data collection schedule for screening and follow-up.

6.2. Screening visit

Formal screening begins once the participant and his/her parent have signed the HIPAA authorization and consent or child assent for screening and enrollment in the NAFLD Pediatric Database 2 study. The participant is considered to be registered in the pediatric Database 2 study once the consent is signed and the Registration Form has been completed. Consent for enrollment may be conducted at standard of care clinic visits, or over the phone with eligible participants, who may receive the consent (at a clinic visit or mailed) to review prior to the registration visit. Recording of data on NAFLD Database 2 study forms may begin once the consent and authorization forms are obtained.

The screening visits may be conducted over two or more study visits. Clinical centers may alter the order of screening procedures done on a particular visit to meet the center's or participant's needs. The last screening visit may be combined with enrollment for the convenience of the participant. This visit schedule allows flexibility in completion of screening procedures, however, a participant will be enrolled only if the data system shows that the participant is eligible, has signed the consent statement, and has had all required screening forms keyed to the data system. Activities at initial screening visit include:

- Signature on the NAFLD Database 2 parent consent, pediatric assent, as needed, and genetic consent form
- Signature on NAFLD Database 2 pediatric study HIPAA authorization form
- Assignment of NASH CRN participant identification number (only for new pediatric participants, continuing participants retain their current ID)
- Medical and medication history
- Habitual beverage intake assessment (Beverage Questionnaire [BEVQ-15])
- Physical examination including vital signs, height, weight, anthropometric measurements, acanthosis nigricans, liver signs, and Tanner staging
- Alcohol use history (Alcohol Use Disorders Identification Test [AUDIT]) for participants 12 years or older, if any prior history of alcohol use is stated
- Review status of liver biopsy data
- Order etiologic tests if needed
- Instruct participant to bring to second screening visit his/her health history information or related materials
- Participant or the guardian to sign medical records release to obtain prior reports and

biopsy slides

- Participant to provide location and contact information
- Coordinator to register participant on clinic data system
- Coordinator to request prior reports and biopsy slides from health care provider
- Fasting blood draw for specimen banking (either screening visit-see below)
- Schedule liver biopsy, if needed
- Schedule second screening visit

The second screening visit should ideally be timed to coincide with the standard of care liver biopsy and is the encounter at which the participant has blood drawn for outstanding laboratory tests and specimen banking. The participant must attend this visit after a 12 hour fast. Blood for serum and plasma banking may be drawn immediately prior to the liver biopsy, but cannot be obtained in the 72 hour period after a liver biopsy. The goals for achieving optimum timing of blood draws for serum and plasma banking are that at least 50% of enrollees will have these biosamples obtained within \pm 30 days of the enrollment liver biopsy, while the remaining 50% will have these drawn within \pm 90 days of liver biopsy. Standard of care procedures are described in manuals of Standard Operating Procedures V: Standard of Care for Pediatric Participants with Fatty Liver Disorders and Standard Operating Procedures I: Pediatric Clinical Center Operations.

Procedures at the second screening visit include:

- Hematology
- Clinical chemistry
- HbA1c
- Hepatic panel
- Fasting lipid profile and fasting glucose and insulin levels
- Fasting blood (serum, plasma) for specimen banking
- Liver biopsy (if needed)
- Provision of pediatric standard of care educational materials (delay providing these to participant until confirmed eligible for the pediatric Database 2 study)

Procedure for combining screening visits

Efficient compression of the enrollment visit schedule can be accomplished by centering initial data and serum and plasma sample collection around the performance of a scheduled standard of care liver biopsy. An overnight stay in a General Clinical Research Center (GCRC) or similar research unit may be used if a clinically indicated biopsy can be undertaken within these premises. Day 1: study questionnaires completed, physical examination, history data obtained; labs drawn including serum and plasma for banking (if fasting; can be done prior to the liver biopsy on day 2 if necessary). Day 2: Liver biopsy performed in the morning. If standard of care biopsy cannot be undertaken in the research unit, coordination with the outpatient procedure center will be necessary for the participant to be discharged from the research unit on the morning of Day 2 and transferred to the clinical procedure facility for the liver biopsy.

6.3. Liver histology requirements

For a new participant to be enrolled in the pediatric Database 2 study, the participant must have a recent liver biopsy that is available for review by the NASH CRN pathologist, and the NASH CRN pathologist must confirm that the biopsy is not exclusionary (i.e., evidence of liver disease not related to NAFLD – see SOP IV: Liver Biopsy and Histology Scoring System, section 4.2.8). A liver biopsy may be obtained as part of standard of care (e.g., for diagnosis or follow-up) as determined by the site investigator during screening. Ideally, this biopsy will be obtained within 30 days of the serum and plasma sample collection, but must be obtained no more than 120 days prior to enrollment and within 90 days of the serum and plasma collection. Liver biopsies will be performed primarily for histological purposes, with the additional goal of obtaining liver tissue, in excess of that needed for histology, from the same biopsy pass, for snap freezing in liquid nitrogen (expression library/cDNA production, proteomics, lipidomics). The procedures for collection and processing of liver biopsy materials are detailed in the NAFLD Database 2 Standard Operating Procedures IV: Liver Biopsy and Histology Scoring System.

6.4. Follow-up visits

The pediatric Database 2 study annual follow-up study visits will be scheduled at 48 week intervals after enrollment. The date of enrollment is when all screening procedures are completed and eligibility checks are fulfilled for study entry, and will be the date from which the follow-up visits are timed (i.e., time zero). Each follow-up visit will have a time window around the target date for the visit; the time window is an interval of months during which the study visit may be completed, and the data collected at the visit may be used to fulfill the data collection requirements for the visit. Data or serum and plasma samples collected outside the allowable time window for a visit are not useable as data for the visit. Each visit has an ideal date for the visit, a lower window date (opening date for the window) and an upper window date (closing date for the window). The dates for a specific participant are specified on the NAFLD Pediatric Database 2 study visit time windows sheet for the participant. This sheet is generated by the clinic data system when a participant is enrolled in the pediatric Database 2 study; it can also be obtained from the NASH CRN data system.

Procedures and forms to be completed at each of the follow-up visits are:

- Follow-up medical history (medication changes, key events or interventions, surgeries, hospital admissions, new diagnoses of co-morbidities, complications of liver disease [variceal bleeding, ascites, edema, hepatic encephalopathy])
- Physical examination
- Habitual beverage intake assessment (Beverage Questionnaire [BEVQ-15])
- Laboratory data (hematology, glucose and insulin, clinical chemistry, hepatic panel, HbA1c, lipid profile)
- Interim drinking history (Alcohol Use Disorders Identification Test - Consumption [AUDIT-C]), for patients 12 years or older
- Blood collection for plasma and serum banking
- Documentation of any additional liver biopsies performed as part of standard of care

6.5. Database 2 contents

Baseline medical history. The NAFLD Pediatric Database 2 study forms will capture whether the participant was ever diagnosed with NAFLD, dates of biopsies, abbreviated weight history, family history (siblings and parents; particularly of obesity and liver disease), demographic history, past medical or surgical events, illness history (including diabetes, gestational diabetes, hypertension, lipodystrophy, polycystic ovarian syndrome), other co-morbid conditions including previously diagnosed lipid and metabolic disease-related conditions (hypercholesterolemia, hypertriglyceridemia), and all diagnoses related to previous liver disease as well as other diagnoses of major organ systems.

Baseline medication history. Pediatric Database 2 case report study forms will capture selected medications taken within 3 months prior to entry. Specific medications queried will include those taken for the treatment of liver disease, diabetes, insulin resistance, hypertension, and hyperlipidemia. Any known medication allergies will be documented.

Follow-up medical history. Follow-up health history will include data on medication changes; key events or interventions, surgeries, hospital admissions; new diagnoses of comorbidities; complications of liver disease [variceal bleeding, ascites, edema, hepatic encephalopathy], liver cancer, other cancer.

Beverage intake. The objective of the beverage intake survey is to estimate the patient's habitual consumption of beverages and the amount of daily calories and grams of sugar consumed from these beverages. The Beverage Questionnaire (BEVQ-15) is administered at baseline and at yearly follow-up visits. The BEVQ-15 is a 15-item questionnaire asking how often and the amount each type of beverage is consumed during the past month. The estimated patient burden is 10 minutes to complete the survey.

Physical examination. Initial and subsequent exams will include: vital signs [temperature, pulse, respiratory rate, blood pressure], anthropometrics [height, weight (without shoes or heavy clothing), waist (at umbilicus), and hip circumference measurements]; general signs [lipodystrophic body habitus, muscle wasting, acanthosis nigricans]; liver signs [jaundice, spider angiomas, palmar erythema, hepatomegaly, splenomegaly, asterixis,]; and Tanner staging.

Alcohol consumption. The objective of the alcohol use data collection is to estimate recent quantity of alcohol ingestion. The AUDIT is a 10-item questionnaire with a simple scoring scale. The Alcohol Use Disorders Identification Test (AUDIT) questionnaire will be administered at baseline to patients 12 years or older; an interim drinking history (AUDIT-C) will be obtained at yearly follow-up visits as part of the follow-up medical history.

Laboratory tests. All laboratory items listed may be obtained from the participant's chart or should be collected as part of the standard of care. Acceptable time intervals between the collection of laboratory items and the pediatric Database 2 study registration will be specified on the data collection forms; for follow-up visits, the laboratory blood draws must be done within the visit window. The blood draw date of the laboratory test must be recorded on the data form.

NAFLD Pediatric Database 2 Protocol**6. Schedule of visits and procedures**

Hematology: Hemoglobin, hematocrit, mean corpuscular volume (MCV), red blood cell count (RBC), white blood cell count (WBC), and platelet count.

Clinical chemistry and HbA1c: Creatinine, total protein, blood urea nitrogen (BUN), uric acid, and hemoglobin A1c (HbA1c).

Hepatic panel: Total bilirubin, direct bilirubin, aspartate aminotransferase (AST), alanine aminotransferase (ALT), alkaline phosphatase, gamma glutamyltransferase (GGT), albumin, prothrombin time (PT), and international normalized ratio (INR).

Fasting lipid profile and glucose-insulin levels: Fasting is defined as nothing by mouth except water and medications for at least 12 hours prior to blood draw. Lipid profile will include fasting triglyceride and cholesterol (total, low-density lipoprotein and high-density lipoprotein cholesterol). Please note whether on lipid medication when lipid profile blood was drawn. If in doubt about fasting status, the test should be repeated. The fasting blood glucose and insulin must be measured on the same blood draw and can be drawn at the same time as the lipid profile.

The tests listed below are required only during screening for new participants.

Screening etiologic tests: Hepatitis B surface antigen, hepatitis C antibody.

Ceruloplasmin and alpha-1-antitrypsin level (plus phenotype if below normal).

Autoantibody studies: anti-nuclear antibody (ANA), antismooth muscle antibody (ASMA), anti-liver/kidney microsomal antibody (Anti-LKM1)
Thyroid Stimulating Hormone (TSH)

6.6. Serum, plasma, DNA, and liver tissue for banking

Fasting serum and plasma, DNA, and any available snap frozen liver tissue will be banked in the NAFLD Pediatric Database 2 study. Blood will be drawn for serum and plasma banking during screening and yearly visits on all participants enrolled in the pediatric Database 2 study. Standardized methods for serum, plasma, DNA, and liver tissue processing that allow for maximal preservation of banked specimens and storage in designated -70 degrees C freezers will be applied across all clinical centers or at the NASH CRN central repository (see NAFLD Pediatric Database 2 Standard Operating Procedures I: Clinical Center Operations).

NAFLD Pediatric Database 2 Protocol

7. Statistical and design considerations

This is a clinicopathologic condition-based database designed primarily to allow the compilation of data and collection of specimens for the purpose of the study of the epidemiology and natural history of NAFLD in children. The study also aims to recruit patients for participation in randomized, controlled therapeutic trials. The recruitment goal is a database of 850 pediatric participants with NAFLD with at least 96 weeks of follow-up.

The primary and secondary objectives of the NAFLD Pediatric Database 2 study, as specified in Sections 2.1 and 2.2 of the protocol, are intentionally very broad. Since this is the largest and most comprehensive prospective study of NAFLD in children, it is expected that many, as yet unasked, questions related to the etiology, natural history, diagnosis, treatment, and prevention of NAFLD will be answered.

Addressing the questions that arise in connection with the NAFLD Database 2 will require the full gamut of statistical analysis procedures, from survival analysis to receiver operating characteristic (ROC) curves. Nearly all questions will require identification of appropriate subgroups of patients from all clinical centers contributing to the NAFLD Pediatric Database 2 study with analyses tailored to the hypothesis or question to be addressed.

This process will be accomplished through formal publication proposals submitted by investigators to the NASH CRN Steering Committee. Each of these proposals must include a justification for the sample size and plan for statistical analysis constructed with the help of the Data Coordinating Center. Each proposal must contain the following information:

- Specification of the primary and secondary outcome variables
- Specification of subgroups of special interest when making treatment comparisons (e.g., males vs. females or ethnic/racial subgroups)
- Specification of baseline covariates or methods to be used to select the covariates for adjustment of treatment comparisons
- Specification of methods for dealing with missing values or lost to follow-up
- Specification of primary and confirmatory analytic methods to be used

Since the NAFLD Pediatric Database 2 study will generate longitudinal data over time, analytic methods must account for, as applicable, time to events, repeated measurements, counts, or other discrete responses. For time to event data, we will use the Cox proportional hazards regression model with covariates tailored to the hypothesis under investigation. For hypotheses involving repeated measurements, events, counts or other discrete responses, we will use either of two approaches: (1) generalized linear models with generalized estimating equations (GEE) with robust variance estimation to account for the clustering; or, (2) multilevel generalized linear mixed models with random coefficients to account for within patient clustering as well as other sources of variations like clinic effects.

NAFLD Pediatric Database 2 Protocol

8. Human research participant issues

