10.3. Whole blood draw schedule

Procedure	Study visit (week)											Total
	Screening	t048	t096	t144	t192	t240	t288	t336	t384	t432	t480	
Fasting glucose and insulin	5	5	5	5	5	5	5	5	5	5	5	55
Fasting lipid	5	5	5	5	5	5	5	5	5	5	5	55
Complete blood count	5	5	5	5	5	5	5	5	5	5	5	55
Clinical chemistry	5	5	5	5	5	5	5	5	5	5	5	55
Hepatic panel	5	5	5	5	5	5	5	5	5	5	5	55
HbA1c	5	5	5	5	5	5	5	5	5	5	5	55
Plasma	10	10	10	10	10	10	10	10	10	10	10	110
Serum	30	20	20	20	20	20	20	20	20	20	20	230
Genetics	10	-	-	-	-	-	-	-	-	-	-	10
Other screening*	20	-	-	-	-	-	-	-	-	-	-	20
Total	100	60	60	60	60	60	60	60	60	60	60	700

All Database 2 study visits are fasting visits and need to be scheduled for early morning. Fasting is defined as nothing by mouth except water in the 12 hours prior to blood draw.

* Etiologic tests as needed

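### Section 10.3 fixes one research-banking blood volume for all participants aged 2 to 17, and the protocol sets no weight-based limit (minor)

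*Protocol*

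**What the plan says.** Section 5.2 of the protocol sets the age range for new participants: "Age at least 2 years of age and not older than 17 years during the consent process". The same range applies to continuing participants, and neither section 5.2 nor section 5.3 sets a minimum weight.

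Section 6.6 makes banking universal: "Blood will be drawn for serum and plasma banking during screening and yearly visits on all participants enrolled in the pediatric Database 2 study". The volumes stand in section 10.3, headed "Whole blood draw schedule". It has one column per visit and no division by age or weight:

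- Screening: serum 30, plasma 10, genetics 10.
- Each of ten follow-up visits: serum 20, plasma 10.

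The table prints no unit. The document history (section 10.5) describes these volumes in mL.

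Some parts of the schedule are flexible, but not the serum and plasma rows. The footnote "Etiologic tests as needed" belongs to the 20 mL row for other screening tests. Section 6.5 lets routine laboratory results come from the chart or from standard of care. The genetics tube depends on its own consent (section 5.4): "There will be a separate consent for the collection, storage, and use of DNA for genetic research".

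For new participants, section 5.2 also makes sampling an entry criterion: "Collection of biosamples (serum, plasma, DNA, and, if available, liver tissue) within 90 days prior to enrollment". It fixes the type of sample and its timing but no volume.

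**The concern.** Blood for banking is taken for research and not for the child's care, so it is the part of the draw that can be cut without affecting clinical management. Followed as written, the schedule takes the same serum and plasma volume from the lightest two-year-old as from the heaviest adolescent.

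The protocol already collects what is needed to do otherwise. Section 6.2 lists among the initial screening procedures "Physical examination including vital signs, height, weight, anthropometric measurements, acanthosis nigricans, liver signs, and Tanner staging", so weight is measured at the first visit. The same list allows the banking draw at either screening visit: "Fasting blood draw for specimen banking (either screening visit-see below". Weight is not used to set the draw.

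A site with a small child is also not told whether a smaller sample is acceptable. This matters most for new participants (650 of the planned 850), for whom sample collection is a condition of entry. Sites under different review boards could settle the question differently.

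At stake are participant burden and consistency between sites. Sample size, power and the analysis are not affected.

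**Working it through.** **1. Reproduce the table in section 10.3.**

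- Screening: six routine rows at 5 mL, plus plasma 10, serum 30, genetics 10 and other screening 20: 6 × 5 + 10 + 30 + 10 + 20 = 100 mL.
- Follow-up: 6 × 5 + 10 + 20 = 60 mL.
- Whole schedule: 100 + 10 × 60 = 700 mL.

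All three agree with the printed totals.

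**2. Separate the banking part.** Routine laboratory rows (30 mL) and other screening tests (20 mL) are left out, because the protocol allows chart or standard-of-care results for the first and makes the second conditional.

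- Serum and plasma over the screening period: 30 + 10 = 40 mL.
- With the genetics tube: 40 + 10 = 50 mL.
- Each follow-up visit: 20 + 10 = 30 mL.

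**3. Express it per kg.** The formula is volume divided by body weight. The protocol gives no weights, so these are assumptions: 12 to 20 kg for the smallest eligible children, and 30 kg as a check because young children with suspected NAFLD may be heavy for their age.

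| Draw | 12 kg | 20 kg | 30 kg |
|---|---|---|---|
| Screening, serum and plasma (40 mL) | 40/12 = 3.3 | 40/20 = 2.0 | 40/30 = 1.3 |
| Screening, with genetics (50 mL) | 50/12 = 4.2 | 50/20 = 2.5 | 50/30 = 1.7 |
| Each follow-up visit (30 mL) | 30/12 = 2.5 | 30/20 = 1.5 | 30/30 = 1.0 |

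All entries are mL/kg. For contrast, 40 mL in a 100 kg adolescent is 40/100 = 0.4 mL/kg, about one eighth of the value at 12 kg (100/12 = 8.3). The follow-up figures fall as a child grows.

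**The case against.** The strongest reply is that no harm is shown. The documents contain no blood-volume threshold against which 3.3 or 4.2 mL/kg could be called too much. They give no age or weight distribution either, so it is unknown whether any child of 12 to 20 kg will enrol. New participants need a clinically indicated biopsy, and section 4.1 ties primary NAFLD to obesity and insulin resistance among other associations, so the lightest weights may be rare. These objections stand, and they keep the point minor.

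A second reply is that a limit may sit elsewhere. Section 6.6 refers to operating procedures, and section 8.1 requires local review-board approval before screening starts. Those documents are not at hand and may well contain a cap. However, section 6.6 cites the procedures for processing and storage and not for volume. The protocol sets the volumes itself in section 10.3, so a limit, or a reference to one, belongs there.

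Three stronger readings are tempting, and the documents do not support them:

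- **Every participant gives 50 mL at one sitting.** The draw that section 6.6 applies to all participants is 40 mL of serum and plasma; genetics needs separate consent. Screening may span several visits and up to 90 days, so 40 or 50 mL is a total for the period and not necessarily a single draw.
- **The schedule breaches a safety limit.** None is stated in the protocol, and none is used here.
- **A child who gives a smaller sample is ineligible.** Section 5.2 sets no volume, so a reduced sample is not ruled out. The protocol just does not say that it is acceptable.

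Reducing the draw also has a cost. Expanding the serum, plasma and DNA bank is a primary objective, and a cap works against it in the smallest children.

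**Conclusion.** The point holds as a minor one. The protocol states a flat rule: 40 mL of serum and plasma over screening (50 mL with genetics) and 30 mL per follow-up visit, for all ages from 2 to 17. Its own allowances for routine and etiologic tests do not reach the serum and plasma rows. This is a rule the protocol fixes, not a detail it leaves open.

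The volumes in mL are exact and come from section 10.3. The per-kg sizes rest entirely on the assumed weights, and the 12 kg end is the least certain. The number of children affected is unknown and may be small. Whether a limit already applies through documents not shown cannot be determined. What can be said is that the protocol states none and gives sites no rule for a small child.

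**What to change.** Add three statements to section 10.3:

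- The listed volumes are maxima, subject to a per-kg limit that applies at each visit and across all screening draws together. Use the limit agreed with the review boards or set in the operating procedures, and cite it if it already exists.
- When the limit binds, banking tubes are reduced first.
- A reduced-volume serum and plasma sample satisfies the biosample criterion in section 5.2.

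Which banking tube to cut first is for the sponsor to choose. No change to the DNA part of section 5.2 is proposed.

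The cost is a short amendment, or a single cross-reference if a limit is already in force. No new measurement is needed, because weight is already taken at screening. The price is fewer banked aliquots from the smallest children, who are likely to be a small part of the cohort, though the protocol does not give their number.
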